12.2.1.1 Suspected Adverse Reaction (SAR)

Any adverse event for which there is a reasonable possibility that the investigational drug or investigational study therapy regimen caused the adverse event. For the purposes of safety reporting, 'reasonable possibility' means there is evidence to suggest a causal relationship between the drug and the adverse event. A suspected adverse reaction implies a lesser degree of certainty about causality than adverse reaction, which means any adverse event caused by a drug (21 CFR 312.32(a)).

12.2.2 Unexpected Adverse Event

An adverse event or suspected adverse reaction is considered "unexpected" if it is not listed in the *Investigator Brochure or package insert* or is not listed at the specificity, severity or rate of occurrence that has been observed; or is not consistent with the risk information described in the general investigational plan or elsewhere in the IND. Any event not listed as a known risk for the aspirin challenge will be considered an unexpected adverse event.

12.2.3 Serious Adverse Event (SAE)

An adverse event or suspected adverse reaction is considered "serious" if, in the view of either the investigator or Sponsor or DAIT/NIAID, it results in any of the following outcomes (21 CFR 312.32(a)):

1. Death.
2. A life-threatening event: An AE or SAR is considered "life-threatening" if, in the view of either the investigator or Sponsor or DAIT/NIAID, its occurrence places the subject at immediate risk of death. It does not include an AE or SAR that, had it occurred in a more severe form, might have caused death.
3. Inpatient hospitalization or prolongation of existing hospitalization.
4. Persistent or significant incapacity or substantial disruption of the ability to conduct normal life functions.
5. Congenital anomaly or birth defect.
6. Important medical events that may not result in death, be life threatening, or require hospitalization may be considered serious when, based upon appropriate medical judgment, they may jeopardize the subject and may require medical or surgical intervention to prevent one of the outcomes listed above.

Elective hospitalizations or hospital admissions for the purpose of conduct of protocol mandated procedures are not to be reported as an SAE unless hospitalization is prolonged due to complications.

12.3 Grading and Attribution of Adverse Events

12.3.1 Grading Criteria

The study site will grade the severity of adverse events experienced by the study subjects according to the criteria set forth in the National Cancer Institute's Common Terminology Criteria for Adverse Events (CTCAE) Version 4.0. This document (referred to herein as the NCI-CTCAE manual) provides a common language to

describe levels of severity, to analyze and interpret data, and to articulate the clinical significance of all adverse events. The NCI-CTCAE has been reviewed by the, *Principal Investigator*, and has been deemed appropriate for the subject population to be studied in this protocol.

Adverse events will be graded on a scale from 1 to 5 according to the following standards in the NCI-CTCAE manual:

Grade 1 = mild adverse event.

Grade 2 = moderate adverse event.

Grade 3 = severe and undesirable adverse event.

Grade 4 = life-threatening or disabling adverse event.

Grade 5 = death.

Events grade 2 or higher will be recorded on the appropriate AE case paper CRF report form for this study.

For grading an abnormal value or result of a clinical or laboratory evaluation (including, but not limited to, a radiograph, an ultrasound, an electrocardiogram etc.), a treatment-emergent adverse event is defined as an increase in grade from baseline or from the last post-baseline value that doesn't meet grading criteria. Changes in grade from screening to baseline will also be recorded as adverse events, but are not treatment-emergent. If a specific event or result from a given clinical or laboratory evaluation is not included in the NCI-CTCAE manual, then an abnormal result would be considered an adverse event if changes in therapy or monitoring are implemented as a result of the event/result.

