4.3. Exclusion Criteria

Individuals who meet any of these criteria are not eligible for enrollment as study participants:

1. Inability or unwillingness of a participant to give written informed consent or comply with study protocol
2. Hypersensitivity to montelukast
3. Current use of zileuton (which blunts the peak levels of urinary LTE₄ during reactions)
4. Any history of bleeding diathesis or current use of anticoagulant/antiplatelet drugs
5. Any history of gastrointestinal bleeding
6. Current use of oral beta blockers, though ophthalmic formulations are acceptable

7. The use of an additional non-steroidal anti-inflammatory drugs (NSAIDs), except the aspirin dosing as detailed for the study
8. Use of any biologic therapy within the prior 4 months (120 days) of Visit 1.
9. History of cardiac rhythm disturbances.
10. Heart rate of <50 bpm at Screening Visit, or evidence of any type of heart block on ECG at Screening Visit.
11. Pregnant, nursing, or planning to become pregnant.
12. Past or current medical problems or findings from physical examination or laboratory testing that are not listed above, which, in the opinion of the investigator, may pose additional risks from participation in the study, may interfere with the participant's ability to comply with study requirements or that may impact the quality or interpretation of the data obtained from the study.
13. Evidence of liver failure (AST or ALT levels >3x normal at Screening)
14. Evidence of kidney failure (creatinine levels >1.5mg/dl in women and >1.7mg/dl in men)

5. Known and Potential Risks and Benefits to Participants

5.1. Risks of Investigational Product or Intervention as cited in Investigator Brochure or Package Insert

Risks of Ifetroban:

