Ifetroban was the subject of 24 controlled and uncontrolled human pharmacology and pharmacokinetic studies. It was also the subject of eight placebo-controlled clinical trials for various cardiovascular indications which are summarized in **Table 2**. The incidence rate of adverse events was generally comparable between the ifetroban-treated subjects and the placebo-treated subjects. Bradycardia was reported more often in the ifetroban group (N=32; 3.3%) than with placebo (N=7; 1.2%). Gastrointestinal events tended to occur more often in the ifetroban subjects than in the placebo subjects, although incidence rates were too small to suggest a trend or pattern. The most frequently reported adverse events (N; % ifetroban vs. N; % placebo) were headache (N=80; 8.4 vs. N=47; 7.7), musculoskeletal pain (N=48; 5.0 vs. N=19; 3.1), angina pectoris (N=33; 3.5 vs. N=22; 3.6), bradycardia (N=32; 3.3 vs. N=7; 1.2), myocardial infarction (N=28; 2.9 vs. N=18; 3.0), nausea/vomiting (N=25; 2.6 vs. N=10; 1.6), dyspepsia (N=24; 2.5 vs. N=9; 1.5), upper respiratory infection (N=24; 2.5 vs. N=9; 1.5), hematoma (N=23; 2.4 vs. N=8; 1.3), coronary artery bypass (N=22; 2.3 vs. N=10; 1.6), coronary angioplasty (N=21; 2.2 vs. N=10; 1.6), abdominal pain (N=20; 2.1 vs. N=10; 1.6), and anxiety/nervousness (N=19; 2.0 vs. N=9; 1.5). All remaining events occurred at a rate less than 2.0% in both treatment groups except for dizziness which occurred in 2.1% (N=13) of placebo-treated subjects (ifetroban: N=13; 1.9%).

Table 2. Number of subjects exposed to ifetroban in clinical studies.

		Subject Exposure	
		Ifetroban	Placebo
Clinical Pharmacology/Pharmacokinetics			
	Human Pharmacology	189	49
	Pharmacokinetic	154	0
Clinical Trials			
	Silent Ischemia (CV124-008)	58	55
	Stable angina (CV124-009)	105	52
	Unstable angina (CV124-011)	315	166
	PTCA (CV124-012)	90	35
	PVD (CV124-014)	137	44
	Post MI (CV124-015)	149	149
	Forearm blood flow in HF (CV124-018)	20	23
	Venous ulcers (CV139-001)	82	83
	Total Subjects	1299	656

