12.3.2 Attribution Definitions

The relationship, or attribution, of an adverse event to the study therapy regimen or study procedure(s) will initially be determined by the site investigator and recorded on the appropriate AE paper case report form (AE/SAE paper CRF). Final determination of attribution for safety reporting will be determined by DAIT/NIAID. The relationship of an adverse event to study therapy regimen or procedures will be determined using the descriptors and definitions provided in Table 12.3.2.

For additional information and a printable version of the NCI-CTCAE manual, consult the NCI-CTCAE web site: <http://ctep.cancer.gov/reporting/ctc.html>.

Table 12.3.2 Attribution of Adverse Events

Code	Descriptor	Definition (guidelines)
UNRELATED CATEGORY		
1	Unrelated	The adverse event is clearly not related to study. The event is completely related to an etiology other than the study product or study intervention (the alternative etiology must be documented in the study subject's medical record)
2	Unlikely	The adverse event is doubtfully related to study and likely to be related to factors other than study product or study intervention.
RELATED CATEGORIES		

3	Possible	The adverse event may be related to study. There is an association between the event and the administration of study product and there is a plausible mechanism for the event to be related to the study product; there may be also an alternative etiology, such as characteristics of the subject's clinical status and/or underlying disease
4	Probable	The adverse event is likely related to study. There is (1) an association between the event and the administration of study product or study intervention, (2) a plausible mechanism for the event to be related to the study product, and (3) the event could not be reasonably explained by known characteristics of the subject's clinical status and/or an alternative etiology is not apparent
5	Definite	The adverse event is clearly related to study. There is (1) an association between the event and the administration of the study product or study intervention, (2) a plausible mechanism for the event to be related to the study product, and (3) causes other than the study product have been ruled out and/or the event re-appeared on re-exposure to the study product

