12.4.3 Recording Adverse Events

Throughout the study, the investigator will record adverse events and serious adverse events as described previously on the appropriate paper case report form (AE/SAE paper CRF) regardless of the relationship to study therapy regimen or study procedure.

Once recorded, an AE/SAE will be followed until it resolves with or without sequelae, or until the end of study participation, or until 14 days after the subject prematurely withdraws (without withdrawing consent)/or is withdrawn from the study, whichever occurs first.

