12.8 Review of Safety Information

12.8.1 Medical Monitor Review

The DAIT/NIAID Medical Monitor shall receive monthly reports from the *Principal Investigator* compiling new and accumulating information on AEs, SAEs, and pregnancies recorded by the study site on appropriate paper CRFs.

In addition, the Medical Monitor shall review and make decisions on the disposition of the SAE and pregnancy reports received by the *Principal Investigator* (See *Reporting of Serious Adverse Events to Sponsor*, and *Pregnancy Reporting*).

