12.8.3 DSMB Review

12.8.3.1 Planned DSMB Reviews

The Data and Safety Monitoring Board (DSMB) shall review safety data at least yearly during planned DSMB Data Review Meetings. Data for the planned safety reviews will include, at a minimum, a listing of all reported AEs and SAEs.

The DSMB will be informed of an Expedited Safety Report in a timely manner. DSMB notification will occur as soon as site personnel are aware of the event but no later than 72 hours, which aligns with the requirements set forth by institutional guidelines.

12.8.3.2 *Ad hoc* DSMB Reviews

In addition to the pre-scheduled data reviews and planned safety monitoring, the DSMB may be called upon for *ad hoc* reviews. The DSMB will review any event that potentially impacts safety at the request of the protocol chair or DAIT/NIAID. In addition, the following events will trigger an *ad hoc* comprehensive DSMB Safety Review:

- Any death that occurs in the study, which is possibly or definitely related to study treatment regimen.
- The occurrence of a Grade 3 or higher related and unexpected SAE in 3 or more of the study participants who have received a study treatment.

After review of the data, the DSMB will make recommendations regarding study conduct and/or continuation.

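### Section 12.3.1 puts only Grade 2+ events on the AE form, so mild on-drug bradycardia, the largest excess in the protocol's ifetroban data, need not be recorded as an AE

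*Combined protocol and SAP*

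**What the plan says.** Section 12.3.1 grades AEs from 1 (mild) to 5 and then sets a floor for recording: "Events grade 2 or higher will be recorded on the appropriate AE case paper CRF report form for this study". For abnormal clinical or laboratory results, the same section says that "a treatment-emergent adverse event is defined as an increase in grade from baseline or from the last post-baseline value". That definition has no Grade 2 floor.

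Several later safety steps depend on what is on the form:

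- Attribution "will initially be determined by the site investigator and recorded on the appropriate AE paper case report form" (12.3.2).
- Follow-up has a condition attached: "Once recorded, an AE/SAE will be followed until it resolves with or without sequelae" (12.4.3).
- The monthly Medical Monitor report is described as "compiling new and accumulating information on AEs, SAEs, and pregnancies recorded by the study site on appropriate paper CRFs" (12.8.1).
- The planned DSMB review receives, at a minimum, "a listing of all reported AEs and SAEs" (12.8.3.1). The ISM receives the same (12.8.2.1).

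Section 12.5.2.1 says, without a grade limit, that all AEs go into the annual DSMB report.

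On heart rate, section 4.3 excludes "Heart rate of <50 bpm at Screening Visit, or evidence of any type of heart block on ECG at Screening Visit". Sections 6.5, 8.3 and 11.2 set no heart-rate criterion after that and leave the matter to the investigator's general discretion. Section 5.1 singles out bradycardia as more frequent on ifetroban than on placebo in the eight earlier placebo-controlled trials.

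**The concern.** The protocol screens people for slow heart rate and heart block before dosing and reports bradycardia as more common on the drug. Yet a new bradycardia judged mild during the four weeks of treatment falls below the stated recording floor. If the site applies that floor, the event is not attributed, has no defined follow-up and is absent from the Medical Monitor's monthly report. It reaches the ISM and DSMB only if someone reports it by another route.

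What is at stake is the completeness of a descriptive safety listing in a single-site trial of about 50 people. No efficacy analysis or powered safety comparison is affected, and the floor applies equally to both blinded arms.

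**Working it through.** **1. Reproduce the protocol's rates.** The eight clinical-trial rows of Table 2 (section 5.1) give the denominators.

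- Ifetroban: 58 + 105 + 315 + 90 + 137 + 149 + 20 + 82 = 956.
- Placebo: 55 + 52 + 166 + 35 + 44 + 149 + 23 + 83 = 607.
- Adding the pharmacology and pharmacokinetic rows gives 956 + 189 + 154 = 1299 and 607 + 49 = 656, the table's totals.
- Bradycardia: 32/956 = 3.35% and 7/607 = 1.15%, against the stated 3.3% and 1.2%.

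**2. Rank the 14 events that section 5.1 gives with counts for both arms.**

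| Event | Ifetroban (of 956) | Placebo (of 607) | Difference, points | Ratio |
|---|---|---|---|---|
| Bradycardia | 32 | 7 | +2.19 | 2.90 |
| Musculoskeletal pain | 48 | 19 | +1.89 | 1.60 |
| Hematoma | 23 | 8 | +1.09 | 1.83 |
| Dyspepsia | 24 | 9 | +1.03 | 1.69 |
| Upper respiratory infection | 24 | 9 | +1.03 | 1.69 |
| Nausea/vomiting | 25 | 10 | +0.97 | 1.59 |
| Coronary bypass | 22 | 10 | +0.65 | 1.40 |
| Headache | 80 | 47 | +0.63 | 1.08 |
| Coronary angioplasty | 21 | 10 | +0.55 | 1.33 |
| Anxiety/nervousness | 19 | 9 | +0.50 | 1.34 |
| Abdominal pain | 20 | 10 | +0.44 | 1.27 |
| Myocardial infarction | 28 | 18 | −0.04 | 0.99 |
| Angina | 33 | 22 | −0.17 | 0.95 |
| Dizziness | 13 | 13 | −0.78 | 0.63 |

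Eleven of 14 are numerically higher on ifetroban. Bradycardia is largest by difference and by ratio. For dizziness the stated 1.9% on ifetroban does not match 13/956 = 1.36%, but either figure is below placebo's 2.1%, so the ranking is unaffected.

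**3. Strength of the bradycardia difference.**

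- Risk ratio 0.0335/0.0115 = 2.90 (computed from unrounded rates).
- SE of the log ratio = √(1/32 − 1/956 + 1/7 − 1/607) = 0.414.
- 95% CI = exp(1.066 ± 1.96 × 0.414) = 1.29 to 6.53.
- Fisher exact p = 0.0071. Bonferroni for 14 events: 0.0071 × 14 = 0.099.
- For comparison, p = 0.07 for musculoskeletal pain and 0.14 for hematoma.

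Pooling the eight trials this way is crude, and all had cardiovascular indications.

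**4. Expected cases in this trial.** Section 13.7 plans 50 recruits and 20 completers per arm, so 20 to 25 people on ifetroban. Assume a rate between the earlier placebo and ifetroban rates. Expected cases are n × rate, and the chance of at least one is 1 − (1 − rate)^n.

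| n | Expected at 1.15% | Expected at 3.35% | Chance of at least one |
|---|---|---|---|
| 20 | 0.23 | 0.67 | 21% to 49% |
| 25 | 0.29 | 0.84 | 25% to 57% |

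These are cases of any grade. The documents do not reproduce the CTCAE 4.0 grading of a low pulse, so the share left unrecorded could be anywhere from 0% to 100%.

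**5. The earlier AERD trial.** Section 1.4 reports a 16-subject trial with no adverse effects. If all 16 took ifetroban, the chance of no bradycardia at a true rate of 3.35% is (1 − 0.0335)^16 = 0.58, and the one-sided 95% upper limit for the rate is 1 − 0.05^(1/16) = 17%. If only 8 did, the figures are 0.76 and 31%. That trial neither confirms nor excludes the excess.

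**The case against.** The strongest reply is that the protocol already captures these events. Section 12.5.2.1 puts no grade limit on what goes to the DSMB each year. After the Grade 2 sentence, 12.3.1 adds that grade changes between screening and baseline are to be recorded too, which can be read to mean that grade increases on treatment are recorded at any grade. Section 12.4.3 could carry that reading forward. This stands as a possible reading. It does not remove the explicit floor a few lines earlier, and 12.4.3 only points back to the earlier text. The result is a conflict in the text, and a site could reasonably follow either side.

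A second reply is that the consequence is small. Fewer than one case is expected. The rate may be lower here, because slow heart rate, heart block, rhythm disturbance and oral beta blockers are excluded. Heart rate should also be captured in the vital signs scheduled in Appendix 1, and exam results go on a CRF (13.1, Source Data). All of this stands, and it is why the point is minor. A pulse value on an exam page is still not an attributed, followed or reviewed AE.

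A third reply concerns bleeding, to which the same floor applies. Here the support is weaker. The hematoma difference is compatible with chance, gastrointestinal bleeding is already a listed ground for discontinuation and withdrawal (6.5, 11.2), bleeding disorders and anticoagulants are excluded (4.3), and section 5.1 reports no significant safety concern in the ifetroban-aspirin studies. Only a pharmacological argument remains: ifetroban prolonged bleeding time, and aspirin is added at Visit 2.

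**Conclusion.** The concern holds as a minor, inexpensive improvement. The Grade 2 floor conflicts with 12.3.1's own definition of a treatment-emergent abnormal result and with 12.5.2.1, so a mild on-drug bradycardia need not be recorded as an AE. The event most exposed to this gap is the one with the largest listed excess in the protocol's own data.

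A reader might infer more than this, and the documents do not support it:

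- *That ifetroban is shown to cause bradycardia.* The adjusted p is about 0.10, the data are pooled cardiovascular trials, and the lead over musculoskeletal pain is 0.3 points (2.19 − 1.89).
- *That heart-rate data will be lost or a signal will be missed.* Vital signs are scheduled, Grade 2+ bradycardia is recorded, and the trial is too small to detect a signal either way.
- *That the absence of a heart-rate rule after Screening leaves participants unprotected.* The investigator may stop treatment at any time, and nothing here supports a new stopping rule.

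The conclusion rests on two assumptions: that the scheduled vital signs include heart rate, and that at least some low-pulse events would be graded 1. The gain is a more complete descriptive listing, with 0.2 to 0.8 bradycardia cases of any grade expected on ifetroban.

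**What to change.** In 12.3.1, after the Grade 2 sentence, add text along these lines: *As an exception, bradycardia is entered on the AE form whatever its grade. A pre-aspirin heart rate under 50 bpm at Visit 2, in a participant whose rate was at least 50 bpm at Visit 1, is entered as bradycardia.* Keep the Grade 2 floor for all other events. Recording mild bleeding or bruising at any grade is optional, on the pharmacological grounds above.

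The change needs a CRF instruction and uses visits and vital signs already scheduled. It adds no measurement, stopping rule or limit on the aspirin challenge. The downside is a few extra AE entries, some of them trivial, such as a shift from 51 to 49 bpm, or minor bruises from blood draws if the optional part is adopted.

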8.2. Screening/Baseline Visit

Screening Visit The purpose of the screening visit is to confirm eligibility to continue in the study.

The following procedures, assessments, and laboratory measures will be conducted to determine participant eligibility:

1. A physical exam
2. Spirometry to assess lung function
3. Lab work (urine pregnancy, liver enzymes (AST and ALT), and creatinine level)
4. Assessment of asthma control (ACQ score, which evaluates asthma control over the proceeding 1 week)
5. Assessment of nasal symptoms (SNOT-22 score, which assesses nasal symptoms over the proceeding 2 weeks)
6. Baseline ECG

The labwork is typically completed within 24 hours of the blood draw. After the Screening Visit there is a 2-week Run-in Period in which subjects will begin taking montelukast 10mg daily (if not already on montelukast as part of their regular asthma care). A telephone encounter (Phone Call 1) 1 week later will ensure safety and confirm stable asthma.

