2. Before aspirin is given, a urine sample will be collected for pregnancy and eicosanoid metabolites, and a nasal fluid and nasal epithelial scraping sample will be taken, along with a blood draw for CBC/differential and cellular assays.
3. Subjects will then undergo an oral aspirin desensitization procedure. They will receive an initial 40.5 mg dose of aspirin, and then every 90 minutes will be given increasing doses of 81, 162, and 325 mg aspirin.
4. Vital signs are obtained every 90 minutes during the aspirin challenge/desensitization.
5. If at any point the subject develops symptoms of a reaction, we will examine them and record the time of onset of reaction. The dose of reaction that induces an increase in TNSS of 2 or more points will be recorded as the provocative dose.
6. Following the onset of reaction, patients will be observed for a 3-hour period, during which time no more aspirin doses will be given. TNSS will be recorded at the onset of reaction and again every 30 minutes during this 3-hour period after reaction.
7. Pulmonary function testing is repeated before each dose and at the onset of reaction and if it remains within 85% of their pre-challenge FEV₁, it will be repeated every 90 minutes during the 3-hour period after reaction. If the FEV₁ falls by 15% or more from their morning pre-challenge FEV₁, they will be treated with

MDI albuterol (up to 8 puffs per administration), followed by nebulized albuterol if needed and FEV₁ will be repeated every 30 minutes until it has returned to within 85% of their morning pre-challenge FEV₁.

8. No medications (except albuterol and ipratropium) will be used for relief of symptoms during the desensitization until the 3-hour period of observation following onset of reaction is completed, unless required for a patient's safety.
9. A blood sample will be collected 1 hour after the onset of reaction for CBC/differential, platelet activation assays, and platelet-leukocyte aggregate measurements. Urine and nasal fluid samples will be collected 90 minutes after the onset of reaction, or if there is no clinical reaction at all, will be collected 90 minutes after the 325mg dose of aspirin is given.

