11.4. Follow-up after Early Study Withdrawal

If a subject needs to discontinue any of the investigational drugs prior to the end of the study, we will ask him/her to come in for one final visit. During this visit we will ask them to return all unused medication, have one final blood draw (to make sure their complete blood count (CBC) is normal), and one final pregnancy test (if applicable). If the subject does not return for this final visit, a study investigator will attempt to speak to the subject by telephone, and if unreachable at their preferred contact number, a clear message regarding the importance of follow-up and study investigator contact information will be left. If a subject experiences an adverse event that results in discontinuation from the study, we will follow the subject until the event is resolved or until the subject is discharged to alternate care.

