15.3. Privacy and Confidentiality

A participant's privacy and confidentiality will be respected throughout the study. Each participant will be assigned a unique identification number and these numbers rather than names will be used to collect, store, and report participant information. Site personnel will not transmit documents containing personal health identifiers (PHI) to the study sponsor or their representatives.

16. Publication Policy

The ICJME (International Committee of Medical Journal Editors) policy on the publication of study results will apply to this trial.

17. Appendix 1. Schedule of Events

Schedule of Events	Study Phase	Screen	Run-In	Treatment Period			Follow-up	
	Week	0	1	2	3	6	7	8
	Visit	V0	Phone Call 1	V1	Phone Call 2	V2	Phone Call 3	Phone Call 4
Procedures/Assessments								
	Informed Consent, Verify eligibility	+						
	Randomization (ifetroban/placebo)			+				
	Physical Exam and vital signs	+		+		++		
	Baseline symptoms (ACQ, SNOT-22)	+		+		+		
	Spirometry	+		+		++		
	Start montelukast	+						
Urine for:	Pregnancy test	+		+		+		
	Eicosanoids			+		++		
Blood for:	CBC/differential	+		+		+		
	Creatinine, LFTs	+						
	Platelet/WBC studies			+		++		
	Nasal washings/scrape samples			+		++		
	FeNO			+		+		
	Aspirin desensitization					+		
	Acute sinonasal symptoms (TNSS)					++		
	Initiation of aspirin therapy					+		
	Adverse event assessment		+	+	+	+	+	+

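### AST, ALT and creatinine are scheduled only at Screening, so protocol testing cannot yield a treatment-emergent liver or kidney laboratory AE, and a listing without one means not measured

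*Combined protocol and SAP*

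**What the plan says.** The Screening tests in Section 8.2 are "Lab work (urine pregnancy, liver enzymes (AST and ALT), and creatinine level". In Appendix 1 (Schedule of Events) the row "Creatinine, LFTs" carries one mark, in the Screen (V0) column. The values have a stated use there: Section 4.3 excludes on "Evidence of liver failure (AST or ALT levels >3x normal at Screening", and on creatinine above sex-specific limits.

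No later draw includes chemistry. Visit 1 blood (Section 8.3) is for a blood count with differential and for cellular assays. Before aspirin at Visit 2, nasal and urine samples are taken "along with a blood draw for CBC/differential and cellular assays". The sample one hour after reaction onset is for a blood count and platelet assays. At the early-withdrawal visit (Section 11.4) subjects "have one final blood draw (to make sure their complete blood count (CBC) is normal", plus a pregnancy test where applicable. The source-data list names blood counts and pregnancy tests but no chemistry.

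Section 12.3.1 gives the grade-increase rule for laboratory and other test results: "a treatment-emergent adverse event is defined as an increase in grade from baseline or from the last post-baseline value". It adds: "Changes in grade from screening to baseline will also be recorded as adverse events, but are not treatment-emergent". It also sets a recording threshold: "Events grade 2 or higher will be recorded on the appropriate AE case paper CRF report form for this study".

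**The concern.** A rule based on a change in grade works only where a test is repeated. Blood counts are repeated, so it can work for them. Liver enzymes and creatinine are not, although the protocol screens and excludes on both and states in Section 1.4 that ifetroban is eliminated primarily by metabolism and biliary excretion.

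What is at stake is how the safety record is read. The Independent Safety Monitor and the DSMB receive listings of reported AEs (Sections 12.8.2.1 and 12.8.3.1). A listing without hepatic or renal laboratory events looks the same whether nothing happened or nothing was tested. In a small placebo-controlled trial of 4 weeks of dosing, a reader could take that silence as reassurance.

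**Working it through.** The plan states no figure on this point, so the main check is a count of scheduled values.

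**Step 1. Scheduled AST, ALT and creatinine values per subject** (Sections 8.2, 8.3 and 11.4; Appendix 1)

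| Time point | Blood drawn for | Chemistry values |
|---|---|---|
| Screening | Eligibility | 1 |
| Visit 1 (randomisation) | Blood count, cellular assays | 0 |
| Visit 2, pre-aspirin (end of 4 weeks) | Blood count, cellular assays | 0 |
| Visit 2, 1 hour after reaction onset | Blood count, platelet assays | 0 |
| Early-withdrawal visit | Blood count | 0 |

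Scheduled values after the first dose: 0.

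**Step 2. Apply the Section 12.3.1 rule.** The protocol uses the word baseline in two ways. Section 8.2 is headed Screening/Baseline Visit, while Section 8.3 calls Visit 1 the baseline visit.
- If Visit 1 is baseline, chemistry has neither a baseline nor a later value.
- If Screening is baseline, chemistry has a baseline but no later value.

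On either reading, scheduled testing gives the rule nothing to compare.

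**Step 3. Arm size.** Section 13.7 recruits 50 subjects to have 40 complete, 20 per arm, allowing 10-20% dropout. At the upper figure, 40 / (1 − 0.20) = 50, which agrees. An arm therefore has 20 completers, or 25 with no dropout.

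**Step 4. What one Visit 2 value would buy.** With 0 events in n subjects, the exact one-sided 95% upper bound on the event rate is 1 − 0.05^(1/n).
- n = 20: 1 − 0.05^(1/20) = 13.9%
- n = 25: 1 − 0.05^(1/25) = 11.3%

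Under the current schedule n = 0 and no bound exists.

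The documents give no hepatic or renal event rate, so a range is assumed. The chance of at least one event in an arm of 20 is 1 − (1 − p)^20:

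| Assumed true rate p | Chance of at least 1 event in 20 |
|---|---|
| 1% | 18% |
| 2% | 33% |
| 5% | 64% |
| 10% | 88% |
| 20% | 99% |

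**Step 5. Unscheduled detection.** Section 12.4.2 also lets AEs come from observation, interview, complaint, the hospital record or an abnormal result. Let q be the share of true cases found that way (assumed). The chance that 40 subjects still show none is (1 − pq)^40. With p = 10%:
- q = 5%: 0.995^40 = 82%
- q = 10%: 0.990^40 = 67%

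An empty listing would thus be likely under these assumptions even if one subject in ten were affected, but it is not certain.

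**The case against.** The strongest reply is that nothing here is broken. Section 12.3.1 is a general grading rule that also mentions radiographs and ultrasounds, which the plan does not schedule. It grades whatever results exist and promises no chemistry. The text and the Schedule of Events agree that chemistry is done at Screening, where it serves eligibility. This stands: there is no contradiction between passages, and the point is a gap in coverage.

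A reader might go further and infer that liver and kidney AEs are bound to come out as zero in both arms. The documents do not support that. Symptomatic or incidentally tested cases can be recorded (Section 12.4.2), AE assessment is scheduled at every contact from Phone Call 1 onward, and no AE table by arm is planned. What is missed is the asymptomatic laboratory change.

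A reader might also infer that the protocol shows a liver or kidney hazard. It does not. In Section 5.1.1, increased liver weights were seen in rat dams at 100 and 1000 mg/kg, and kidney changes at 750 and 1000 mg/kg, with no drug-related change in dams at 10 mg/kg. Section 5.1 counts 1299 subjects exposed to ifetroban and names no hepatic or renal event among the most frequent AEs. That record does not fill the gap either, because it reports no chemistry results. The earlier AERD trial of 16 subjects is said to have shown no adverse effects, without saying whether chemistry was measured.

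Nor does the start of aspirin support the point. A draw taken before aspirin says nothing about aspirin.

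Finally, the gain is small. Grade 1 changes fall below the AE recording threshold. Laboratory work typically takes up to 24 hours (Section 8.2), so a Visit 2 result may arrive after the challenge and would not protect anyone during treatment. Both remarks are correct, and they limit the value of the change to description.

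**Conclusion.** The point holds as a low-cost improvement. Chemistry is scheduled once, before randomisation. Protocol-scheduled testing therefore cannot produce a treatment-emergent hepatic or renal laboratory AE, and the absence of one in the safety listings carries no information about asymptomatic changes.

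One Visit 2 value would replace a denominator of 0 with a randomised comparison of about 20 per arm. With no events among 20 to 25 ifetroban subjects, rates above 13.9% to 11.3% would be excluded. Rare toxicity would stay out of reach: at an assumed true rate of 2%, the chance of seeing any event in 20 subjects is 33%.

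The conclusion rests on the schedule as written and on the planned arm sizes. The event rates and the share of cases found without scheduled testing are assumptions. Whether the sponsor holds other on-drug chemistry data for ifetroban cannot be judged from these documents.

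**What to change.** Add AST, ALT and creatinine to the pre-aspirin blood draw already taken at Visit 2 and to the final draw in Section 11.4. Mark them at Visit 2 in the Schedule of Events. State in Section 12.3.1 that the Screening value is the chemistry baseline for the grade-increase rule. That sentence would also give any unscheduled result a defined comparator.

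The cost is three assays on existing draws for about 50 subjects, and occasional incidental abnormal results to follow up. No new visit or venepuncture is needed. Eligibility and the primary endpoint do not change, and no dose, stopping or management rule is proposed.

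If the sponsor prefers to leave the schedule alone, one sentence saying that hepatic and renal laboratory values are not assessed on treatment would prevent the misreading.
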